### 8.6 ASSESSMENT WINDOWS

For any data summarized by scheduled visit, an analysis visit window will be used. The scheduled visits, as recorded on the eCRFs, and the corresponding target days and study day intervals are specified in Table 8-4. The analysis visit window will be derived based on the information specified in Table 8-4.

In the protocol, the visit window for Week 4, Week 8, Week 12, and Week 16 is  $\pm 5$  days and the visit window for the Week 15 visit is  $\pm 5$  days and at least 24 hours prior to Week 16 6MWT. In order to allow slotting of discontinuation visits and visits outside the planned schedule, the visit windows have been expanded for analysis purposes for Week 4, Week 8, Week 12, and Week 16. The nominal study visit identified as Week 15 in the eCRF will be used for the Week 15 visit provided it is at least 24 hours prior to Week 16 6MWT or there is no Week 16 visit.

Visit	Target Study Day	Study Day Interval
ECGs, SGRQ:		
Baseline	1	Study Day ≤1 (prior to the date of the first dose)
Week 16	113	1 < Study Day
PFTs, Clinical laboratory as	ssessments and NT-proF	BNP:
Baseline	1	Study Day $\leq 1$ (prior to the first dose)
Week 8	57	$1 < $ Study Day $\leq 71$
Week 16	113	99 < Study Day
Peak 6MWT:	·	
Baseline	1	Study Day ≤1 (prior to the first dose)
Week 4	29	$1 < $ Study Day $\leq 43$
Week 8	57	$43 < $ Study Day $\leq 71$
Week 12	85	$71 < $ Study Day $\leq 99$
Week 16	113	99 < Study Day
Trough 6MWT:		
Week 15	106	Nominal study visit and at least 24 hours prior to Week 16 6MWT or no Week 16 visit
Vital signs, Pulse oximetry:		
Baseline	1	Study Day $\leq 1$ (prior to the first dose)
Week 4	29	$1 < $ Study Day $\leq 43$
Week 8	57	$43 < $ Study Day $\leq 71$
Week 12	85	$71 < $ Study Day $\leq 99$
Week 15	106	Nominal study visit and at least 24 hours prior to Week 16 6MWT or no Week 16 visit
Week 16	113	99 < Study Day

 Table 8-4
 Assessment Windows for Scheduled Visits

Note: Study Day = (Assessment Date) - (First Dosing Date) +1

Abbreviations: 6MWT, 6-Minute Walk Test; ECG, Electrocardiogram; NT-proBNP, N-Terminal pro-brain natriuretic peptide; PFT, Pulmonary function test.

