Abbreviations: ECG, electrocardiogram; NT-proBNP, N-terminal pro-brain natriuretic peptide; PFTs, pulmonary function tests; PH, pulmonary hypertension; SGRQ, St. George's Respiratory Questionnaire; 6MWT, 6-minute walk test; 6MWD, 6-minute walk distance; CT, computed topography; SpO₂, saturation of peripheral capillary oxygenation; HR, heart rate; eCRF, electronic case report form; FEV1, forced expiratory volume in 1 second; FVC, forced vital capacity; TLC, total lung capacity; DLCO, lung diffusion capacity; AE, adverse event; SAE, serious adverse event; 6MWD, 6-minute walk distance; ET, early termination

- ^a Screening Visit assessments can occur up to 30 days prior to the first dose of study drug. Baseline assessments can occur up to 48 hours prior to the first dose of study drug to allow for scheduling of all activities; however, the Baseline 6MWT must be performed prior to randomization. Screening and Baseline assessments may be combined if all entry criteria are satisfied within 48 hours prior to the first dose of study drug. Baseline PFTs, 6MWT, and CT scan (if a historical scan within 6 months is not available) assessments used to determine eligibility criteria must be performed prior to randomization. Sites should provide a completed Pre-Baseline review form to the Medical Monitor which will be reviewed, signed, and returned to the site prior to randomization.
- b The visit window for Week 4, Week 8, Week 12, Week 15, and Week 16 is ± 5 days. The Week 16 visit must occur at least 24 hours after the Week 15 visit.
- c For the Screening and Baseline Visits, the subject must be evaluated for and meet all inclusion/exclusion criteria.
- d Vital signs must be collected after 5 minutes of rest (seated); no other measurements or procedures should be performed during this 5-minute period. When possible, vital signs should be collected prior to the 6MWT. If vital signs cannot be obtained prior to the 6MWT then they should be obtained after recovery from the 6MWT.
- ^e Blood for NT-proBNP assessment must be drawn prior to conducting the 6MWT and will occur prior to randomization at Baseline (or as part of the Screening Visit assessment if the Screening and Baseline Visits are combined).
- f For subjects consenting to the optional biomarker sample.
- g For subjects consenting to the optional whole genome sequencing sample.
- h For females of childbearing potential.

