- All AEs will be documented from the time of informed consent until the time screen failure is documented, or until the subject is either discontinued from the study or all Week 16 study assessments have been completed and should be followed until either resolution (or return to normal or base line values), until they are judged by the Investigator to no longer be clinically significant, or for at least 30 days if the AE extends beyond the final study visit (Week 16).
- On Hospitalizations due to cardiopulmonary indications must be recorded in the eCRF from the time of informed consent until study termination. Adverse events resulting in hospitalizations, regardless of cause or duration, should also be recorded as SAEs per Appendix 15.2.
- P Exacerbations of underlying lung disease; defined as an acute, clinically significant, respiratory deterioration characterized by evidence of new widespread alveolar abnormality (see Section 3.3.2.10). Exacerbations will also be recorded as AEs or SAEs per Appendix 15.2.
- ^q Time to clinical worsening will be measured from the time of randomization until 1 of the following criteria are met: hospitalization due to a cardiopulmonary indication; decrease in 6MWD > 15% from Baseline directly related to the disease under study, at 2 consecutive visits and at least 24 hours apart; death (all causes); or lung transplantation.
- ^r Once all entry criteria have been met and the randomized treatment assignment confirmed, the first dose of study drug (3 breaths; 18 mcg) will be inhaled in the clinic, followed by at least a 1 hour observation period (Defined as Day 1).
- Subjects who permanently discontinue study drug during the 16-week Treatment Phase are encouraged to undergo premature termination assessments prior to discontinuing study drug and are required complete all remaining scheduled study visits through Week 16 (excluding the Week 15 Visit) to be eligible for entry into the open-label study.
- ^t The premature termination of study drug visit should be conducted prior to study drug discontinuation or as close as possible to the last dose of study drug.

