3.3.2.4.1 Clinical Chemistry and Hematology

Blood for the measurement and evaluation of clinical chemistry and hematology, will be collected at the Screening and Baseline Visits prior to administration of study drug and repeated at Week 8 and Week 16 or ET to assess for treatment-emergent changes in clinical chemistry and hematological laboratory parameters. Values for the following parameters will be obtained:

Electrolyte Panel Chemistry Panel Hematology Panel Sodium Total bilirubin Hemoglobin Potassium Alkaline phosphatase Hematocrit Bicarbonate Alanine aminotransferase Red blood cell count Chloride Aspartate aminotransferase • Red blood cell morphology Urea nitrogen White blood cell count Creatinine Platelet count Calcium Albumin

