3.3.2.5 Pulmonary Function Tests

Pulmonary Function Tests will be assessed at Baseline and repeated at Week 8 and Week 16 or ET. Baseline PFTs are to be conducted prior to randomization and after recovery from the 6MWT. The Week 8 and Week 16 or ET PFTs should be conducted after recovery from the 6MWT. If the PFTs are done both prior to and after a bronchodilator, only the prebronchodilator values will be recorded.

The following parameters will be recorded (absolute values and % predicted): FEV1, FVC, TLC, and DLCO (uncorrected for hemoglobin and lung volume).

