7.6 END OF STUDY (WEEK 16) AND/OR EARLY TERMINATION VISIT

The assessments to be completed during the Week 16 Visit are listed below in the recommended sequence of events. If a decision is made to early terminate a subject from study drug or from the study in its entirety, the following assessments should be conducted as soon as possible and prior to study drug discontinuation, if possible. If the subject permanently discontinues study drug prior to Week 16 for any reason, the subject should be encouraged to remain in the study and complete all visits (excluding the Week 15 Visit) up to and including Week 16:

- SGRQ (questionnaire must be administered prior to any results, procedures, or blood draws)
- PE
- Vital signs (following at least 5 minutes of rest; collected prior to 6MWT or after recovery from the 6MWT); including weight, RR, HR, SBP, DBP, and temperature.
- Documentation of supplemental oxygen requirement (L/min)
- 12-Lead ECG (following at least 5 minutes of rest in the semi-recumbent position)
- Urine pregnancy test, for women of childbearing potential
- Blood draws for clinical laboratory parameters
- NT-proBNP (must be drawn prior to 6MWT; for central laboratory processing only)
- Collection of blood sample for evaluation of biomarkers (optional)
- Peak 6MWT (must be conducted between 10 to 60 minutes after the most recent dose of study drug and following at least 10 minutes of rest [sitting])
- Pulse oximetry (to be performed immediately prior to, throughout the conduct of, and immediately following the 6MWT)
- PFTs (to be performed after recovery from the 6MWT)
- Hospitalizations due to a cardiopulmonary indication
- Exacerbations of underlying lung disease
- Time to clinical worsening will be evaluated as an exploratory endpoint from the time of randomization until 1 of the following criteria are met:
 - Hospitalization due to a cardiopulmonary indication
 - Decrease in 6MWD > 15% from Baseline directly related to disease under study, at 2 consecutive visits and at least 24 hours apart
 - o Death (all causes)
 - Lung transplantation
- AEs
- Concomitant medications
- Study drug accountability

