### 8 GENERAL CONSIDERATIONS FOR DATA ANALYSES

All the data collected in the electronic Case Report Form (eCRF) will be listed. In general, listings will be sorted by treatment group, subject number, and scheduled assessment (if applicable). Listings will include assessment date, assessment time (if available), study day, and all relevant data collected in the eCRFs. For data collected on a fixed schedule, the assessment identifier or the nominal time point will also be included on the listing. Repeat or redundant observations within an assessment window and observations that do not fall within any predefined assessment window (and will, therefore, be excluded from summaries) will be flagged in these listings. Subjects who are not to be included in the analysis population (eg, Safety population, Per-protocol population) will be flagged.

In general, the data will be summarized by scheduled assessment (if applicable) within each treatment group. For continuous variables, summary statistics will include the mean, standard deviation, median, minimum, and maximum. For summaries of non-normal data such as 6MWD, interquartile range (lower quartile, upper quartile) may also be included. Minimums and maximums will be expressed using the level of precision in which the variable was collected. All other statistics will be rounded, using an additional decimal place than was collected. For discrete variables, summaries will include the frequency and percentage in each category. Percentages will be rounded to 1 decimal place. For all inferential analyses and descriptive comparisons, p-values will be rounded to 4 decimal places. Values less than 0.0001 will be denoted as <0.0001, and values greater than 0.9999 will be denoted as >0.9999 whenever practical, categories of discrete variables will be ordered and labelled as they appear in the eCRF, and all categories represented on the case report form will be included in summaries, even when they do not apply to any subjects in the study.

Unless otherwise specified, all statistical tests will be 2-sided at alpha level 0.05. All statistical calculations will be completed using SAS® Version 9.4 or above.

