### Multiple Evaluations within the Same Analysis Window

After all the observations have been slotted based on the table above, if there are multiple valid observations for an assessment within an assigned analysis visit window, only 1 of these observations will be used for summary statistics and analyses. The observation to be used is determined using the following hierarchy (in decreasing order):

- The observation closest to the target study day
- The later observation if 2 observations are equally close to the target study day

For missing values where the LOCF algorithm is applied, it is always the last valid observation on treatment carried forward, even though this might not be the observation obtained by the above hierarchy and used in the summaries by visit window.

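### Table 8-4 has no window on Days 72–99 for PFTs, clinical laboratory tests and NT-proBNP, so early-termination and off-schedule values from those days drop out of the by-visit summaries

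*SAP*

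**What the plan says.** **Windows.** SAP 8.6 applies analysis windows to all data summarized by scheduled visit and gives the reason for their width: "In order to allow slotting of discontinuation visits and visits outside the planned schedule, the visit windows have been expanded for analysis purposes". For PFTs, clinical laboratory tests and NT-proBNP, Table 8-4 lists Baseline, Week 8 (after Day 1, up to and including Day 71) and Week 16 (after Day 99). It has no other post-baseline row for them.

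**Values outside every window.** SAP Section 8 says that "observations that do not fall within any predefined assessment window (and will, therefore, be excluded from summaries") are flagged in the listings.

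**Two values in one window.** One is kept, and the first criterion is "The observation closest to the target study day".

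**What the protocol collects.** Section 3.3.2.5: "Pulmonary Function Tests will be assessed at Baseline and repeated at Week 8 and Week 16 or ET". Section 3.3.2.4.1 has chemistry and hematology "repeated at Week 8 and Week 16 or ET to assess for treatment-emergent changes in clinical chemistry and hematological laboratory parameters". Section 3.3.1.3 sets the same times for NT-proBNP. On the ET visit, Section 7.6 says "the following assessments should be conducted as soon as possible and prior to study drug discontinuation, if possible", and footnote t of the Section 3.2 schedule says that it "should be conducted prior to study drug discontinuation or as close as possible to the last dose of study drug".

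**Where the values are used.** PFTs are summarized by visit (SAP 12.4), laboratory values by visit and in shift tables (SAP 12.5.1, 12.5.2), and NT-proBNP at each assessment (SAP 10.2.2).

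**The concern.** An ET visit can fall on any study day. For these three assessments, one made on Days 72–99 has no row to go to, although the section says that discontinuation visits are what the wider windows are for. The loss is selective: subjects who keep to the schedule never lose a value this way, while those who stop in that month do. PFTs and clinical laboratory parameters are among the assessments that Protocol 3.3.2 treats as primary for safety, and Protocol 10.3.4 lists both for comparison between the groups.

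SAP 12.4 also counts subjects whose FEV1 falls by more than 20% at any visit after Baseline. If that means windowed visits, which the SAP does not say, a fall seen only at an ET visit on Days 72–99 would not be counted.

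**Working it through.** **1. Reproduce the window limits.** The target days in Table 8-4 are 29, 57, 85 and 113. The midpoints are (29+57)/2 = 43, (57+85)/2 = 71 and (85+113)/2 = 99, which are the limits used for the peak 6MWT. The PFT/laboratory/NT-proBNP block has targets 57 and 113 only. It keeps 71 and 99 without the Week 12 row that sits between them. The midpoint of its own targets is (57+113)/2 = 85.

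**2. Assign every study day after Day 1.**

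| Block in Table 8-4 | Post-baseline windows set by study day | Days in no window |
|---|---|---|
| Peak 6MWT; vital signs and pulse oximetry | 2–71 (Weeks 4 and 8), 72–99 (Week 12), 100 onward | none |
| ECG, SGRQ | 2 onward | none |
| PFTs, laboratory tests, NT-proBNP | 2–71, 100 onward | 72–99 |

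Gap: 99 − 72 + 1 = 28 days. From Day 2 to Day 113 there are 112 days, and 28/112 = 25%. The visit label does not rescue these values, because only Week 15 is assigned by nominal visit.

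**3. Check scheduled visits.** Protocol 3.2, footnote b: "The visit window for Week 4, Week 8, Week 12, Week 15, and Week 16 is" ±5 days. Week 8 is therefore 57 ± 5 = Days 52–62 and Week 16 is 113 ± 5 = Days 108–118. Neither touches Days 72–99, so only ET and off-schedule values can fall there.

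**4. Size, by assumption.** The plan gives about 314 subjects and about 15% discontinuation (266/0.85 = 312.9, consistent with its rounded total). Then 0.15 × 314 = 47.1 subjects. Timing and ET attendance are not in the documents. The shares below are assumptions; 25% corresponds to even timing.

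| Subjects with an ET visit | 10% in gap | 25% in gap | 40% in gap |
|---|---|---|---|
| All | 4.7 | 11.8 | 18.8 |
| Three quarters | 3.5 | 8.8 | 14.1 |
| Half | 2.4 | 5.9 | 9.4 |

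**5. Would wider windows alone repair it?** Not fully, because of the closest-to-target rule.

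- *Week 8 extended to Day 99.* An on-time Week 8 value lies 0 to 5 days from Day 57. An ET value on Days 72–99 lies 15 to 42 days away, so it is always discarded when an on-time Week 8 value exists.
- *Cut at Day 85.* ET values on Days 72–85 (15 to 28 days from Day 57) still lose to an on-time Week 8 value. Those on Days 86–99 (14 to 27 days from Day 113) lose to an on-time Week 16 value if the subject returns.
- *Week 16 started at Day 72.* This keeps the ET value only if no Week 16 visit follows, and it labels Day 72 as Week 16.

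The same rule already discards ET values on Days 63–71 (6 to 14 days from Day 57) when an on-time Week 8 value exists. That is 9 days; 9/112 = 8.0%, and 47.1 × 0.080 = 3.8 further ET sets under even timing and full attendance.

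**The case against.** The strongest reply is that little is lost:

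- Protocol 10.3.4 plans no inference on PFTs or laboratory parameters.
- The values remain in flagged listings.
- Clinically significant changes are reported as adverse events (Protocol 3.3.2.4 and Appendix 15.2).
- Subjects who stop drug are encouraged to attend through Week 16 (Protocol 7.6 and 8.1). Those who do still contribute a Week 16 value, so the ET value is lost and not the subject.
- Even timing with full attendance gives about 12 ET sets over both arms, and the inputs to that figure are assumed.

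All of this stands, and it is why the point is minor. It does not remove the conflict between the table and its stated purpose.

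The FEV1 objection also stands in part. An ET visit is a visit after Baseline, so SAP 12.4 can be read as already counting it. The text leaves this open.

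A reader might infer that NT-proBNP escapes because its missing Week 16 value is imputed by LOCF (SAP 8.3.2). That is only partly supported. LOCF does nothing for the summary at each assessment in SAP 10.2.2. For the test, SAP 8.6 carries forward the last valid on-treatment observation even if the within-window hierarchy did not select it. This probably admits a Day 72–99 value, but the SAP does not say that a value in no window counts as valid.

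A reader might also suspect the single post-baseline window for SGRQ and ECG. It matches the protocol's one assessment at Week 16 or ET, and no change is needed there.

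**Conclusion.** The point holds as a minor defect. Followed as written, the SAP omits Day 72–99 values of PFTs, laboratory tests and NT-proBNP from the by-visit summaries and the laboratory shift tables, and possibly from the FEV1 count. The 28-day gap is certain. The number of values is not: about 5 to 19 ET sets if 15% of 314 discontinue, 10% to 40% of them on those days, all with an ET visit; about 12 under even timing; fewer if ET attendance is lower. Off-schedule values on those days are additional and cannot be counted from the documents.

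A reader might infer that the gap hides safety signals or weakens the efficacy result. The documents support neither. The affected safety displays are descriptive, and listings and adverse event reporting remain. The peak 6MWT has a Week 12 window covering the same days, so the primary analysis is unaffected. The NT-proBNP test probably still uses on-treatment values from the gap, subject to the one clarification on validity.

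**What to change.** Before unblinding:

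1. **Add an ET-visit row to Table 8-4** for PFTs, clinical laboratory tests and NT-proBNP. It holds only values collected at the ET visit, whatever the study day. Show it in the by-visit summaries and the laboratory shift tables, and footnote that an ET value may also appear in the Week 8 or Week 16 row. Do not label the row on-treatment, because footnote t of the protocol schedule allows the visit to follow the last dose. The row also keeps the ET values from Days 63–71 that are displaced today.
2. **To slot off-schedule values as well, make the two windows contiguous,** for example with a cut at Day 85. This supplements the ET row and does not replace it.
3. **In SAP 12.4, state that the FEV1 count uses all post-baseline values, windowed or not.** In the same edit, reconcile the threshold: the text counts falls greater than 20%, while the title of Table 14.3.4.7 in SAP 15.1 uses ≥20%.
4. **In SAP 8.6, state that LOCF for NT-proBNP may use an on-treatment value that falls in no window.**

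Cost: one row in Table 8-4 and in the affected outputs, a few clarifying sentences and small reprogramming. No new data are needed. The downside is that some ET values appear in two rows. If step 2 is not taken, off-schedule values in the gap stay in the listings only, apart from the FEV1 count and any on-treatment NT-proBNP value carried forward.

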### 8.3 PREMATURE DISCONTINUATION AND MISSING DATA

#### 8.3.1 Missing Data Handling for 6MWD

For the analysis of 6MWD, subjects may not have completed the treatment with study drug prior to the Week 16 visit for the following reasons: death, progressive disease, AE, withdrawal of consent by the subject, protocol violation, loss to follow-up, termination of study by the sponsor, or withdrawal for other reasons. Every attempt must be made to perform all efficacy assessments immediately prior to premature termination of study drug or withdrawal from the study. In addition, subjects still receiving study drug may be too critically ill to perform the 6MWT, resulting in missing data for that assessment.

Every effort should be made to complete all scheduled study assessments for all randomized subjects. Although attempts will be made to continue to collect data after termination of study drug, these data are being collected for sensitivity analyses and descriptive purposes only. Assessments performed after treatment unblinding or more than 24 hours after the last dose of study drug will not be included in the main analyses of peak 6MWD.

For subjects whose peak 6MWD measures at Week 4, Week 8, Week 12, or Week 16 are missing, the missing value will be imputed as described in Table 8-1.

Reason for missing 6MWD measure	Imputation
Death (all causes)	Worst score (0 meters)
Clinical worsening event	Worst score (0 meters)
Too ill to perform 6MWT	Worst score (0 meters)
All other reasons	Last (peak) Observation Carried Forward (LOCF)

Table 8-1Imputation Rules for Peak 6MWD

Abbreviations: 6MWD, 6-Minute Walk Distance; 6MWT, 6-Minute Walk Test.

For subjects whose trough 6MWD measures at Week 15 are missing, the missing values will be imputed as described in Table 8-2.

Reason for missing 6MWD measure	Imputation
Death (all causes)	Worst score (0 meters)
Clinical worsening	Worst score (0 meters)
Too ill to perform 6MWT	Worst score (0 meters)
All other reasons	Baseline Observation Carried Forward (BOCF)

Table 8-2Imputation Rules for Trough 6MWD

Abbreviations: 6MWD, 6-Minute Walk Distance; 6MWT, 6-Minute Walk Test, BOCF, Baseline observation carried forward.

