# 10.1.1.3 Sensitivity and Subgroup Analyses

In order to analyze walk distances at each scheduled assessment, values for missing or excluded assessments up to and including Week 16 will be imputed according to rules described in Section 8.3.1.

To further support the robustness and assess the sensitivity of the primary efficacy analysis of change in peak 6MWD at Week 16 (provided that the primary analysis yields significant results), the above non-parametric and parametric analyses and summaries will be repeated using each of the following modifications (as data permit):

- The Per-protocol population will be used instead of the ITT population
- Missing data imputation using the LOCF method (based on peak values)
- Missing data imputation using the last rank carried forward (LRCF) method (based on peak values) (O'Brien 2005)
- Using only the observed values without imputation
- Including data collected after termination of the study drug
- ITT population excluding subjects with a reported exacerbation within 3 days of the Week 16 peak 6MWT measure
- Stratified by ILD etiology categories (IIP, CHP, Occupational, CPFE, and Other)
- Stratified by Baseline 6MWD categories (≤350 meters versus >350 meters, ≤median baseline 6MWD versus > median baseline 6MWD)
- Stratified by Baseline DLCO percent predicted (<40% versus  $\geq 40\%$ )
- Stratified by Baseline pulmonary vascular resistance (PVR) (<4 versus  $\geq 4$  WU)
- Stratified by sex (male versus female)
- Stratified by age group (<65 years of age, 65 to <80 years of age, and ≥80 years of age)
- Stratified by study drug dose at Week 16 (0 to 3 breaths, 4 to 6 breaths, 7 to 9 breaths, and 10 to 12 breaths).

A longitudinal data analysis using mixed model repeated measurement (MMRM) will also be performed to estimate the treatment difference in change in peak 6MWD at Week 16. The MMRM will include the change from Baseline in peak 6MWD as the dependent variable, treatment, week, and treatment by week interaction as fixed effects, and Baseline 6MWD as a covariate. An unstructured variance/covariance structure shared across treatment groups will be used to model the within-subject errors. An additional sensitivity analysis will be performed for percent change from Baseline to Week 16 in peak 6MWD using the same approach as the primary analysis method where the percent change from Baseline is calculated as

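### SAP Table 8-4 drops a completed Week 15 trough walk when the Week 16 walk follows within 24 hours, although the later walk cannot have influenced it (low severity)

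*SAP*

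**What the plan says.** SAP 8.6 takes the Week 15 visit as recorded in the eCRF, but conditionally: it is "used for the Week 15 visit provided it is at least 24 hours prior to Week 16 6MWT", or if the subject has no Week 16 visit. The trough row of Table 8-4 repeats the condition: "Nominal study visit and at least 24 hours prior to Week 16 6MWT or no Week 16 visit". The Week 15 row for vital signs and pulse oximetry has the same wording. For the Week 16 peak walk, Table 8-4 asks only that the study day be later than 99.

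The spacing comes from the protocol. Footnote b of Protocol 3.2 states: "The Week 16 visit must occur at least 24 hours after the Week 15 visit". Protocol 3.3.1.1.3.1 asks the same of the Week 16 peak walk. Protocol 3.3.1.1.3.2 and 7.5 put the matching requirement on the trough walk, alongside a minimum of 4 hours since the last dose.

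Three further SAP provisions bear on a walk that fails the condition:

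- SAP 8: "observations that do not fall within any predefined assessment window (and will, therefore, be excluded from summaries) will be flagged in these listings".
- SAP 10.1.1.3: "values for missing or excluded assessments up to and including Week 16 will be imputed according to rules described in Section 8.3.1".
- SAP 10.2.3: missing trough walks are imputed by Table 8-2, and the analysis is repeated using only subjects who have a Week 15 trough value.

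Table 8-2 assigns 0 meters for death, clinical worsening or being too ill to walk. For every other reason it carries the baseline walk forward (BOCF).

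**The concern.** When two walks are too close together, the second may be affected by the first, but the first cannot be affected by the second. Table 8-4 nevertheless removes the first walk and places no spacing condition on the second. The exception for subjects without a Week 16 visit makes this plain: the same trough walk is used if the subject never returns and discarded if the subject returns early. Its use depends on a later event, not on how the walk was done.

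The trough walk is a formally tested secondary endpoint, third and last of the secondaries in the fixed sequence of SAP 8.4. A measured value would be lost and, on the natural reading, replaced by no change. If that happens equally in both arms, the estimated trough difference moves toward zero.

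**Working it through.** **1. Can a short gap occur inside the visit windows?** Protocol 3.2 sets target days 106 and 113, each ± 5 days.

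- Week 15: 106 - 5 = 101 to 106 + 5 = 111.
- Week 16: 113 - 5 = 108 to 113 + 5 = 118.
- Overlap: Days 108 to 111.

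A gap under 24 hours is therefore possible with both visits in window. For example, a trough walk at 13:00 and a peak walk at 10:00 the next day are 21 hours apart. That would still breach the 24-hour requirement, and the target days are 113 - 106 = 7 days apart.

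**2. What happens to the walk?**

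- SAP 8.6: it fails the Week 15 condition.
- SAP 8: it is left out of summaries and flagged in the listing.
- SAP 10.1.1.3: excluded walks are imputed like missing ones. This sentence sits in the section on sensitivity analyses of the peak endpoint, so applying it to the trough walk is an inference.
- SAP 10.2.3 and Table 8-2: exclusion for timing alone fits only the residual category, BOCF. Change = baseline - baseline = 0 m.
- SAP 10.2.3, observed-case repeat: the subject has no accepted Week 15 value, so the walk is not restored.

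**3. The plan's own sample size figure.** The documents give no figure for the 24-hour rule, so this step checks only the inputs reused below. SAP 5 assumes 30 m, SD 75 m, two-sided 0.05 and 90% power.

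- Normal approximation: n per arm = 2 × (1.960 + 1.282)² × 75² / 30² ≈ 131.4, rounded up to 132.
- Two-sample t-test: 132.3, rounded up to 133, which is the plan's 133 per arm (266 in total). Power at 133 per arm is 90.1% (t-test) or 90.4% (normal).
- Discontinuation: 266 / 0.85 = 312.9, so 313 against the stated approximate 314.

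The plan's figure is reproduced.

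**4. Dilution.** Let a fraction f of both arms have the trough change set to 0, unrelated to outcome. Let the true difference be d, the placebo mean change 0 and the SD 75 m.

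- Expected difference = (1 - f) × d.
- Variance, treated arm = (1 - f) × 75² + f(1 - f) × d². Variance, placebo arm = (1 - f) × 75².
- SE = √(sum of the two variances / 157), with 157 = 314 / 2 per arm.
- Power = Φ(expected difference / SE - 1.960).

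For d = 13.7 m, the trough effect of the earlier Phase III PAH study in Protocol 1.2.3, two cases in full:

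- f = 0: SE = √(2 × 5625 / 157) = 8.465; 13.7 / 8.465 = 1.618; power = Φ(-0.342) = 36.6%.
- f = 5%: difference = 13.0 m; SE = √((5352.7 + 5343.8) / 157) = 8.254; ratio = 1.577; power = Φ(-0.383) = 35.1%.

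| f (assumed) | d = 13.7 m: difference | power | d = 30 m: difference | power |
|---|---|---|---|---|
| 0 | 13.7 m | 36.6% | 30.0 m | 94.3% |
| 1% | 13.6 m | 36.3% | 29.7 m | 94.1% |
| 5% | 13.0 m | 35.1% | 28.5 m | 93.2% |
| 10% | 12.3 m | 33.5% | 27.0 m | 91.8% |

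The 30 m column uses the primary planning difference as an upper illustration. Power is for the trough test taken alone, ignoring the need to pass the preceding tests.

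**The case against.** The best defense is that the SAP only enforces the protocol, which requires the trough walk to come at least 24 hours before the Week 16 walk. A walk that misses this is not fully compliant, so calling it simply valid goes too far. That stands, and it means the rule was inherited and not invented in the SAP. It does not justify the discard. The protocol puts the same gap on the Week 16 walk, yet only the earlier walk is removed. SAP 8.6 widens the other windows to retain off-schedule visits. Table 8-4 also does not check the 4-hour condition, which does bear on whether the walk is a trough measure.

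A reader might infer three stronger points that the documents do not support:

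- **That SAP 8.6 itself sets the change to zero.** It only decides which walk is used. The zero comes from Table 8-2, through wording written for the peak endpoint.
- **That breaches are easy or frequent.** The documents give no rate, the targets are a week apart, and the protocol repeats the requirement several times.
- **That the Week 16 walk is accepted without any check.** SAP 8.3.1 excludes peak walks after unblinding or more than 24 hours after the last dose. A short gap classed as a major deviation affecting the primary analysis would also remove the subject from the Per-protocol population (SAP 6 and 9.2). What is missing is a spacing condition.

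The protocol gives no reason for the gap, so fatigue or carry-over is an inference. The point that a later walk cannot alter an earlier one does not depend on it.

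**Conclusion.** The concern holds at low severity. As written, SAP 8.6 and Table 8-4 can discard a completed trough walk because of a later event, and the SAP leaves the replacement value to inference, most naturally a change of 0 m.

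The size is modest: about f times the trough effect. With 13.7 m assumed, power drops by 0.3 percentage points at f = 1%, 1.5 at 5% and 3.1 at 10%. This rests on several assumptions:

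- f is not in the documents.
- Losses are equal in both arms and unrelated to outcome. If they differ by arm, the bias need not be toward zero.
- 13.7 m is a median effect at Week 12 in a different population.
- SD 75 m is the planning value for the Week 16 change.
- 157 per arm ignores the expected 15% discontinuation.

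A reader might infer that the trough result or the primary result is in jeopardy. The documents do not support that. The test is last in the sequence, the primary endpoint does not use the Week 15 walk, equal dilution is conservative, and the discarded values remain in the listings. The Week 15 vital signs and pulse oximetry caught by the same condition are descriptive only.

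**What to change.** 1. In SAP 8.6 and the trough row of Table 8-4, use the nominal Week 15 walk for the trough analysis whenever it precedes the Week 16 6MWT or there is no Week 16 visit. Remove the 24-hour condition. The Week 15 row for vital signs and pulse oximetry can be aligned in the same edit.
2. Record gaps under 24 hours as protocol deviations and flag them in the 6MWT listing.
3. In SAP 10.1.1.3, add a sensitivity analysis of the Week 16 peak endpoint that excludes those subjects' Week 16 walks.
4. In SAP 8.3.1, state outright whether a trough walk excluded for any remaining reason counts as missing under Table 8-2.

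The cost is SAP wording and one extra table, with no new data. The downside is that the SAP would knowingly retain trough walks that miss the protocol's spacing requirement. The flag in the listing makes that visible.
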